### 10.3.2. COVID-19 Adverse Events

If a patient is diagnosed with COVID19 by a positive test result and any of the SAE criteria (Section 10.2) are met, report the event as an SAE. If a patient has a positive test result for COVID19 and is asymptomatic, or is symptomatic but not meeting SAE criteria, it should be reported as an AE.

As with all SAE reporting, the SAE should be reported, per protocol, within 24 hours of becoming aware of the event. If the 24-hour reporting deadline is not met, then a note should be added to the SAE form stating the reason the timeline was not adhered to.

## 10.4. Acute Kidney Injury

KDIGO guidelines for diagnosing AKI are as follows:

- Increased serum creatinine of  $\geq 0.3$  mg/dL ( $\geq 26.5$   $\mu\text{mol/L}$ ) within 48 hours.
- Increased serum creatinine of  $\geq 1.5$  times the baseline (which is known or presumed to have occurred within the prior 7 days),
- Urine volume of  $< 0.5$  mL/kg/h for 6 hours or more (KDIGO 2012).

These KDIGO guidelines typically apply to hospital settings, where baseline values within given timeframes (ie, the preceding 48 hours to 7 days) are available. However, in interventional studies, such as the current study, values this recent will not likely be available in most cases. In such instances, at the Investigator's discretion, diagnosis of AKI may be based on the most recently available serum creatinine level preceding the event, provided that this creatinine measurement was conducted at or after the last study visit prior to the event (ie, was within 3 months prior to the event).

The Investigator should always take into consideration whether the event is true acute deterioration of kidney function due to an identified etiology or whether the event represents natural progression of the underlying kidney disease. In cases of AKI where an etiology is identified, the reported AE term should reflect the etiology for the impairment of renal function (eg, AKI due to hypovolemia).

## 10.5. Serious Renal Conditions

The following conditions should always be reported as SAEs:

- Progression of CKD leading to chronic dialysis: For patients who undergo transition to chronic maintenance dialysis, the verbatim SAE term should be reported as "progression of CKD leading to chronic dialysis." The term "chronic dialysis" should also be captured on the Concomitant Procedure page of the eCRF.
- Medical conditions requiring transient acute dialysis: For patients who undergo transient acute dialysis, the verbatim SAE term should record the condition for which the dialysis is required. For example, if a patient requires acute dialysis due to hyperkalemia, the verbatim SAE term would be reported as "hyperkalemia requiring transient acute dialysis." The "acute dialysis" should also be captured on the Concomitant Procedure page of the eCRF.
- Kidney transplantation: For patients receiving a kidney transplant, the reason for the transplant should be recorded as the verbatim SAE (eg, "progression of CKD requiring kidney transplant"). The term "kidney transplant" should also be captured on the Concomitant Procedure page of the eCRF.

## 10.6. Evaluation of Adverse Events/Serious Adverse Events

### 10.6.1. Causality Assessment

Assessment of the relationship between the AE and exposure to the study medication is important for regulatory reporting and assists in the overall analysis of the safety information. For each AE/SAE the Investigator will determine whether, based on available evidence, there is a reasonable possibility that the study medication caused the event. Causal relationship will be classified according to the following criteria:

- Not Related: There is no suspicion of a causal relationship between exposure and the AE.
- Unlikely Related: There is no evidence for a causal relationship between exposure and the AE; however, such a relationship cannot be ruled out.

- **Possibly Related:** There is some evidence supporting the possibility of a causal relationship between exposure and the AE.
- **Related:** There is strong evidence that there is a causal relationship between exposure and the AE.

A causality assessment will be provided for each AE/SAE recorded even if there is only limited information at the time.

Upon receipt of follow-up information, the Investigator may change his/her assessment of causality and amend the AE/SAE report accordingly.

### 10.6.2. Severity

Severity indicates the intensity of the event and should not be confused with seriousness (ie, [Section 10.2](#)), which is an event outcome applied for the purpose of event classification and regulatory reporting.

The Investigator will assess the severity of all AEs/SAEs as mild, moderate, or severe based on the following definitions:

- **Mild:** A type of AE that is usually transient and may require only minimal treatment or therapeutic intervention. The event does not generally interfere with usual activities of daily living.
- **Moderate:** A type of AE that is usually alleviated with additional specific therapeutic intervention. The event interferes with usual activities of daily living, causing discomfort, but poses no significant or permanent risk of harm to the research participant.
- **Severe:** A type of AE that interrupts usual activities of daily living or significantly affects clinical status or may require intensive therapeutic intervention.

### 10.6.3. Outcome

Outcome describes the status of the AE. The Investigator will provide information regarding the patient outcome of each AE. Definitions for possible results of an AE outcome include the following:

- **Recovered/Resolved:** The event has improved, or the patient recuperated.
- **Recovering/Resolving:** The event is improving.
- **Not Recovered/Not Resolved:** The event has not improved, or the patient has not recuperated.
- **Recovered/Resolved with Sequelae:** The patient recuperated but retained pathological conditions directly resulting from the disease or injury.
- **Fatal:** Termination of life as a result of an AE. There should be only 1 AE marked with this outcome.
- **Unknown:** Not known, not observed, not recorded, or refused.

#### **10.6.4. Action Taken Regarding the Study Medication**

The action taken with regard to the study medication in response to the AE will be provided at the time the event is reported. Options for action taken include the following:

- Drug Withdrawn: Medication schedule was modified by permanently terminating a prescribed regimen of medication.
- Dose Reduced: Medication schedule was modified by subtraction either by changing the frequency, strength, or amount.
- Dose Increased: Medication schedule was modified by addition either by changing the frequency, strength, or amount.
- Dose Not Changed: Medication schedule was maintained.
- Drug Interrupted: Medication schedule was modified by temporarily terminating a prescribed regimen of medication.
- Unknown: Not known, not observed, not recorded or refused.
- Not Applicable: Determination of a value is not relevant in the current context eg, if the AE began and ended prior to treatment or after discontinuation of treatment.

#### **10.6.5. Assessment of Expectedness**

The expectedness of an SAE will be determined by the Sponsor in accordance with the sparsentan Reference Safety Information (which is contained in the Investigator's Brochure) or the irbesartan product label, as applicable.

### **10.7. Reporting Adverse Events and Serious Adverse Events**

#### **10.7.1. Reporting Adverse Events**

AEs (including SAEs) will be captured from the time informed consent is signed to the patient's final visit.

For patients who discontinue study medication (see [Section 6.3.1](#) and [Section 6.3.2](#)) but are not withdrawn from the study, AEs will continue to be recorded until the patient completes the study (see [Section 6.4](#) for definition of patient completion).

If a patient initiates RRT (including transplant) after premature discontinuation of study treatment, only AEs and SAEs considered related or possibly related to study treatment need to be recorded.

AEs will be recorded using MedDRA by System Organ Class and Preferred Term. When recording, it is preferable to provide a diagnosis. In the absence of a diagnosis, each sign and symptom will be captured as a unique AE. Sufficient information should be sought to assist the Investigator both in determining the diagnosis and in making a causality assessment.

Reporting should not be delayed pending receipt of all required information. If information is unavailable at the time of the initial report, the Investigator is expected to follow-up until the required information has been obtained.

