### 10.7.2. Reporting Serious Adverse Events

The necessity and time requirements for reporting of SAEs to the Sponsor or its designee and/or regulatory agencies are as follows:

- All SAEs will be reported by email to the SAE contact on the [Study Contact Information](#) page of this protocol or by fax to the number in the Investigator Site File within 24 hours of the Investigator's first knowledge of the event, regardless of causal relationship.
- A completed SAE Report Form containing a detailed written description of the event along with available supporting documents (eg, discharge summary, autopsy report, and diagnostic test results, etc.) will be provided by email to the SAE contact on the Study Contact Information page or by fax to the number in the Investigator Site File.
- Additional information that is not available at the time the initial SAE Report Form was completed will be promptly reviewed and provided by email to the SAE contact on the Study Contact Information page or by fax to the number in the Investigator Site File within 48 hours of receipt. Full supporting documentation should be solicited by the investigative site even if the SAE occurred at another Institution. Such documentation may include copies of relevant patient/hospital records, discharge summaries, laboratory/test results, or autopsy reports.
- If, at any time after the patient has completed participation in the study (as defined in [Section 6.4](#)), the Investigator or study staff becomes aware of an SAE that they suspect is related to the study medication (see [Section 10.6.1](#)), the event and any known details will be reported promptly by email to the SAE contact on the Study Contact Information page or by fax to the number in the Investigator Site File following the reporting instructions.

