### **8.7. Analysis of Other Secondary and Exploratory Endpoints**

All other secondary and exploratory endpoints will be evaluated using the FAS.

Use of systemic immunosuppressive medication for renal indication will be determined via medical review of concomitant medications and associated indications, and be done prior to each database lock and unblinding.

Kidney-related hospitalizations will be determined via medical review of serious AEs and be performed prior to each database lock and unblinding.

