## 10. SAFETY AND TOLERABILITY

Safety analyses will be conducted using the Safety Analysis Set at both the primary and final analysis. At the primary analysis, all available data will be summarized. Unless otherwise noted, all safety analyses will be conducted using on-study data. All safety analyses specified below refer to the double-blind period only, except where noted. If >5% of patients initiate RRT while on study, select summaries excluding results after initiation of RRT may be prepared.

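### Protocol 10.7.1 lets sites omit unrelated AEs and SAEs when RRT follows drug discontinuation; this contradicts 10.7.2 and 10.1 and can leave on-study safety tables incomplete

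*Protocol*

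**What the plan says.** Five places in the protocol bear on what must be recorded.

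- Section 10.7.1 opens with the general rule: "AEs (including SAEs) will be captured from the time informed consent is signed", and capture runs to the final visit.
- Its second paragraph covers patients who are off drug but still in the study: "AEs will continue to be recorded until the patient completes the study". Under 6.4, completion of the double-blind period means follow-up to Week 114.
- Its third paragraph makes an exception. "If a patient initiates RRT (including transplant) after premature discontinuation of study treatment", then "only AEs and SAEs considered related or possibly related to study treatment need to be recorded". SAEs are named.
- Section 10.7.2 requires every SAE to reach the sponsor within 24 hours of the investigator's "first knowledge of the event, regardless of causal relationship". Section 10.1 collects all AEs, serious or not, from consent to the end-of-study visit.
- Section 10.5 lists progression to chronic dialysis, conditions that need transient acute dialysis, and kidney transplantation under this rule: "The following conditions should always be reported as SAEs".

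The SAP then uses these data. Section 10 runs the safety analyses on on-study data and adds that, if more than 5% of patients start RRT, "select summaries excluding results after initiation of RRT may be prepared". Section 8.7 gives the source for one part of the hospitalization endpoint: "Kidney-related hospitalizations will be determined via medical review of serious AEs".

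**The concern.** A site with a patient who stopped drug, later started dialysis and is then admitted for something judged unrelated has two opposite instructions. Neither 10.7.2 nor 10.1 refers to the exception, and the exception does not say that it overrides them, so sites may collect differently.

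The gap would not fall at random. The exception applies only after RRT, which is a kidney outcome that randomized treatment may affect, and it then filters on the investigator's view of causality. At stake is the completeness of the on-study AE and SAE comparison between arms in patients with the worst kidney outcome, and of the SAE information that the DMC receives. A smaller stake is the exploratory hospitalization endpoint.

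**Working it through.** No sample size, power or alpha figure depends on this point, so the check is a comparison of texts.

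**1. Do the rules conflict?** Take an SAE judged unrelated that occurs after RRT, in a patient who had already stopped drug and remains in follow-up.

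| Rule | Must it be recorded or reported? |
|---|---|
| 10.1 | Yes, as an AE, up to the end-of-study visit |
| 10.7.1, paragraphs 1 and 2 | Yes, up to study completion |
| 10.7.1, paragraph 3 | Not required |
| 10.7.2 | Yes, within 24 hours |
| 10.5, if it is a transplant or a listed dialysis event | Yes, always |

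If paragraph 3 is a specific exception, it overrides 10.7.2 without saying so. If 10.7.2 governs, the SAE part of paragraph 3 has no effect. The text does not decide between them.

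**2. What does the filter let through?** Section 10.6.1 has four causality classes. Only Possibly Related and Related are required under paragraph 3. Unlikely Related, which the protocol defines as a relationship that cannot be excluded, falls outside. The same section lets the investigator revise causality when follow-up arrives, but an event that was never recorded cannot be revised. The SAP takes a more cautious line elsewhere: 6.6.4 counts a missing relationship as related.

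**3. Does the order of events matter?** Yes. A patient who stops drug and later starts dialysis is covered by the exception. A patient who starts chronic dialysis on drug and stops for that reason, which 6.3.2 lists as a ground for stopping, is not covered as the sentence is worded. The same later admission is required for the second patient and optional for the first.

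**4. Who uses the data?**
- SAP 10 and 10.1: the main TEAE and serious TEAE tables use on-study data, and the TEAE definition gives no end date.
- SAP 10.1.3: the on-treatment summaries stop 30 days after last dose for patients who discontinue. They are additional and largely unaffected.
- SAP 10: the post-RRT exclusion is an option, so by default the main tables include post-RRT results.
- Protocol 13.2: at each meeting the DMC reviews a running list that is meant to hold every SAE.

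**5. Hospitalizations.** Frequency and duration are exploratory (Protocol 6.1.2). Kidney-related stays come from SAE review (SAP 8.7). The source for any-cause stays is not given. No counting window is stated.
- Rate model: Protocol 12.7.4 adjusts for exposure to randomized treatment, and SAP 8.7.5 uses log exposure as an offset. This suggests counting over the treatment period, in which case stays after discontinuation and RRT do not count under either recording rule.
- Duration ANCOVA (Protocol 12.7.4, SAP 8.7.3): no offset and no treatment limit. If on-study stays are counted, unrecorded SAEs are lost here.
- Logistic analysis of hospitalization frequency (Protocol 12.7.4): also no stated window.

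**6. How many patients?** The documents give no expected number with RRT after discontinuation. The only related figure is the SAP trigger: 0.05 × 380 = 19, so more than 5% means at least 20 patients starting RRT at full enrolment. That is a condition for an optional table, not a forecast, and it does not separate RRT before discontinuation from RRT after it.

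**The case against.** The best defence is that paragraph 3 is a deliberate, specific exception placed directly after the general rule, and that it says only what is needed, not what is forbidden. A site that follows 10.7.2 still reports every SAE. This stands in part: loss is possible, not certain. It does not remove the conflict, because paragraph 3 names SAEs and 10.7.2 has no matching exception.

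Several stronger readings are tempting, and the documents do not support them.

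- A reader might infer that deaths disappear. Death is a reason for leaving the study and is recorded as such (Protocol 6.5), and SAP 7.1 tabulates discontinuation reasons by arm. The death stays visible, although its adverse event record may be missing.
- A reader might infer that transplants disappear. Section 10.5 also captures them on the procedure page, and SAP 10.3 collects procedures to the final visit.
- A reader might infer that the composite of 40% eGFR reduction, ESRD or death is damaged. Starting RRT is itself an ESRD event, and patients without an event are censored no later than treatment discontinuation (SAP 8.7.4.1). It is largely unaffected.
- A reader might infer that hospitalizations are removed from the endpoint. That depends on the unstated window, and the exposure adjustment points away from it for the rate model.
- A reader might infer that one transient acute dialysis session triggers the exception. RRT is not limited to chronic dialysis in 10.7.1, so this is open. But 10.5 has a separate term for acute dialysis, and 6.1.1.3 uses RRT to define ESRD, so maintenance dialysis or transplant is the more natural meaning.
- A reader might infer that the arm with more kidney failure will look better. The documents contain no rates from which to show it.

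**Conclusion.** The conflict is in the text and should be resolved. A site that follows the third paragraph of 10.7.1 as written can omit unrelated and unlikely-related SAEs after RRT. The on-study TEAE and serious TEAE tables and the DMC's SAE list can then be incomplete, with the gap selected by a kidney outcome and by causality opinion. Kidney-related hospitalizations may also be lost, mainly from the duration analysis, if stays are counted on study.

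The size cannot be stated. It depends on how many patients start RRT after stopping drug, how long they remain in follow-up, and which rule their sites apply. The group may well be small. For the double-blind period the window closes at Week 114, since patients who stop drug permanently cannot enter the extension (7.2.1). Bias between arms is possible in either direction and is not shown. No confirmatory test is at stake. This is a change the sponsor should make for SAE completeness.

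**What to change.** Reconcile 10.7.1 with 10.7.2 and 10.1. Either delete the RRT sentence or limit it to non-serious AEs. State that all SAEs, including hospitalizations and deaths, are recorded to the patient's final visit regardless of causality, of RRT, and of whether RRT came before or after drug discontinuation. If a limited exception for non-serious AEs is kept, define RRT for that purpose.

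In the SAP, keep the optional summaries without post-RRT results as the sensitivity view, and state the source and counting window for any-cause and kidney-related hospitalizations.

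The cost is one amended protocol sentence, a note to sites and a short SAP clarification, with slightly more SAE reporting for what is probably a small number of patients. Events not recorded at the time may be hard to recover later, so the site note should not wait for the next full amendment if local rules allow.

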### 10.7.2. Reporting Serious Adverse Events

The necessity and time requirements for reporting of SAEs to the Sponsor or its designee and/or regulatory agencies are as follows:

- All SAEs will be reported by email to the SAE contact on the [Study Contact Information](#) page of this protocol or by fax to the number in the Investigator Site File within 24 hours of the Investigator's first knowledge of the event, regardless of causal relationship.
- A completed SAE Report Form containing a detailed written description of the event along with available supporting documents (eg, discharge summary, autopsy report, and diagnostic test results, etc.) will be provided by email to the SAE contact on the Study Contact Information page or by fax to the number in the Investigator Site File.
- Additional information that is not available at the time the initial SAE Report Form was completed will be promptly reviewed and provided by email to the SAE contact on the Study Contact Information page or by fax to the number in the Investigator Site File within 48 hours of receipt. Full supporting documentation should be solicited by the investigative site even if the SAE occurred at another Institution. Such documentation may include copies of relevant patient/hospital records, discharge summaries, laboratory/test results, or autopsy reports.
- If, at any time after the patient has completed participation in the study (as defined in [Section 6.4](#)), the Investigator or study staff becomes aware of an SAE that they suspect is related to the study medication (see [Section 10.6.1](#)), the event and any known details will be reported promptly by email to the SAE contact on the Study Contact Information page or by fax to the number in the Investigator Site File following the reporting instructions.

### 10.7.3. Follow-up of Adverse Events and Serious Adverse Events

**All AEs** will be followed until resolution, until the condition stabilizes, or until completion of the patient's participation or study termination, whichever occurs first.

**SAEs** will be followed until resolution, until the condition stabilizes, or until the Investigator and the Sponsor agree that follow-up is no longer necessary.

All AEs/SAEs documented at a previous visit/contact where event outcome is designated as not recovered/not resolved, recovering/resolving, or unknown will be reviewed by the Investigator at subsequent visits/contacts. SAEs that are ongoing after completion of the last scheduled visit will continue to be followed to determine the final outcome.

Rules for AE/SAE follow-up apply to all patients to the extent allowed by the patient's consent. The Investigator will ensure that follow-up includes further investigations consistent with appropriate medical management to understand the nature and/or causality of the AE/SAE. The Sponsor, its designee, or regulatory authorities may also request additional information regarding an AE/SAE at any time.

All follow-up information will be promptly reviewed by the Investigator and provided by email to the SAE contact on the Study Contact Information page of this protocol or by fax to the

number in the Investigator Site File within the specified timelines. Additional AEs/SAEs may be identified during the review of follow-up information and will be processed in accordance with requirements defined throughout [Section 10](#).

